# A double-blind, placebo-controlled, within-group randomised, first-in-human, single-centre trial to evaluate the safety, tolerability and pharmacokinetics of single and multiple ascending oral doses of C106 in healthy male and female subjects

The following amendments have been made to the first regulatory approved version of this Clinical Trial Protocol (version 2.0).

Type of change	Summary of changes	Revised protocol version
Substantial amendment	The proposed doses for the remaining planned SAD cohorts are 240 mg and 300 mg.	Version 2.0
	The maximum daily dose of C106 is changed from 200 mg (100 mg BID) to 480 mg (240 mg BID). One (1) cohort is added to the MAD part (cohort B:4).	
	The pre-dose ECG recordings will be done on Day 1 instead of Day- 1.	
	ECG recordings and vital signs assessments will be done 40 minutes post-dose instead of 1-hour post-dose in order to perform the assessments closer to the assumed $C_{max}$ timepoint, as recommended by the iSRC.	
	Risk-assessments regarding COVID-19 has been updated according to current recommendations.	
Substantial amendment	An exploratory, non-invasive pharmacodynamic (PD) assessment of endothelial function will be performed using EndoPAT in Part B, cohort B:4 before the first IMP administration (Day -1 or Day 1) and 30±10 minutes after IMP administration on Day 7.	Version 3.0
	The Sponsor address has been updated.	
	The planned trial period has been extended until Q3 2023.	

# 1 TRIAL SYNOPSIS

# Trial title

A double-blind, placebo-controlled, within-group randomised, first-in-human, single-centre trial to evaluate the safety, tolerability, and pharmacokinetics of single and multiple ascending oral doses of C106 in healthy male and female subjects.

Trial code	EudraCT No
VP-C106-101	2021-006014-36
Planned trial period	Phase of development
Q2 2022 to Q3 2023	1, first-in-human (FIH)

### Trial design

This is a FIH, double-blind, placebo-controlled, within-group randomised, trial designed to evaluate the safety, tolerability, and pharmacokinetics (PK) of single and multiple ascending oral doses of compound 106 (C106) in healthy females of non-childbearing potential and healthy males.

The trial will be conducted in 2 parts:

Part A, single ascending dose (SAD) including a food interaction cohort: safety, tolerability, and PK in healthy males and healthy females of non-childbearing potential receiving single ascending doses of C106.

Part B, multiple ascending dose (MAD): safety, tolerability, and PK in healthy males and healthy females of non-childbearing potential receiving twice daily multiple ascending doses of C106 for 8 days.

### Objectives

# **Primary objective**

To evaluate the safety and tolerability of single and multiple oral doses of C106 in healthy subjects.

### Secondary objectives

- To characterise the PK of single and multiple oral doses of C106 in plasma and urine of healthy subjects.
- To evaluate the effect of a high fat meal on PK after a single oral dose of C106 in healthy subjects (Part A).

### **Exploratory objectives**

- To evaluate the metabolite profile of C106 in plasma of healthy subjects at steady state (Part B)
- To estimate the excreted C106 and its metabolites, and the metabolite profile of C106 in urine of healthy subjects at steady state (Part B).

- To collect and store electrocardiogram (ECG) data for potential future evaluation of the effect of C106 on ECG parameters, including concentration-QTc analysis using Expert Precision QT (EPQT) assessment (Part A)
- To evaluate the pharmacodynamic (PD) effect of C106 on endothelial function in healthy subjects at steady state (Part B, cohort B4).

# Endpoints

### **Primary endpoints**

- Treatment Emergent adverse events (AEs) and serious AEs (SAEs).
- Clinically relevant changes in:
  - 12-lead electrocardiograms (ECGs).
  - Vital signs (blood pressure, heart rate (HR), body temperature and respiratory rate
  - Laboratory safety variables (haematology, coagulation, clinical chemistry, and urine analysis).
  - Physical examination.

# Secondary endpoints

### Part A

[figure not shown]
- PK parameters:
  - Area under the plasma concentration *vs*. time curve (AUC) from time 0 to infinity (AUCinf) and AUC from time 0 to the time of the last quantifiable concentration (AUClast,).
  - Plasma half-life associated with the terminal elimination phase  $(T_{\frac{1}{2}(z)})$ , maximum plasma concentration  $(C_{max})$ , and time to  $C_{max}$   $(T_{max})$ .
  - $\circ$  Total clearance of the drug from plasma following oral administration (CL/F) and apparent volume of distribution associated with the terminal elimination phase (Vz/F).
  - % of dose excreted unchanged in urine and renal clearance.
  - Relative bioavailability of C106 in fasted versus fed conditions.
- Dose proportionality after a single oral dose based on  $AUC_{inf}$  and  $C_{max}$ .

### Part B

- PK parameters after the first dose:
  - $\circ$  AUC over the dosing interval (AUCtau), AUCinf, T1/2(z), Cmax, Tmax, CL/F, Vz/F.
- PK parameters after the last dose:
  - AUC at steady state (AUCtau),  $T_{\frac{1}{2}(z)}$ ,  $C_{max}$ ,  $T_{max}$ , CL/F,  $V_z/F$ .
- Dose proportionality (based on AUCtau and Cmax) and accumulation ratios (based on AUCtau and Cmax).
- % of dose excreted unchanged in the urine and renal clearance.
- Observed concentration at the end of a dosing interval, immediately before next administration (Ctrough).

# **Exploratory endpoints**

- Metabolite In Safety Testing (MIST) analysis of the metabolite profile in plasma in comparison with the metabolite profile in plasma from non-clinical safety studies.
- Profile of excreted metabolites in urine. Cardiodynamic ECG parameters.
- Change from baseline in reactive hyperemia index (RHI) and augmentation index (AI) scores at Day 7 as measured by EndoPAT.

### Number of subjects planned

Approximately 160 subjects will be screened to achieve 80 randomised subjects.

**Part A:** 48 subjects will be randomised and dosed in 6 cohorts (Cohorts A1 to A6, each of 8 subjects with 6 subjects receiving C106 and 2 subjects receiving placebo).

**Part B:** 32 subjects will be randomised and dosed in 4 cohorts (Cohorts B1 to B4, each of 8 subjects with 6 subjects receiving C106 and 2 subjects receiving placebo).

If indicated by emerging data and recommended by the internal safety review committee (iSRC), 2 cohorts (8+8 subjects) may be added to Part A, and 1 cohort (8 subjects) may be added to Part B.

### Diagnosis and main eligibility criteria

- Healthy females of non-childbearing potential and healthy males, 18 to 65 years of age.
- Has provided signed informed consent.
- Body mass index (BMI)  $\geq 18.5$  and  $\leq 30.0$  kg/m^2.
- Agree to use sufficient contraception as defined in this clinical trial protocol (CTP).
- Good general health and fulfilling all the inclusion criteria and none of the exclusion criteria.

### Methodology

This is a double-blind, placebo-controlled, within-group randomised, FIH trial in which the safety, tolerability, and PK of orally administered C106 will be assessed in healthy subjects. The trial consists of 2 parts: a SAD part (Part A) and a MAD part (Part B). One cohort participating in Part A will receive C106 under both fasted and fed conditions to investigate the effect of a high-fat meal on the single dose PK of orally administered C106.

### Part A (SAD):

In Part A, single, oral doses of C106 will be administered in 6 sequential dose cohorts, each of 8 subjects. Within each cohort, subjects will be randomised to receive either C106 (n=6) or placebo (n=2) in the fasted state. The proposed doses are: 5, 30, 60, 180, 240 and 300 mg C106. Up to 2 additional dose cohorts can be explored based on emerging safety, tolerability and PK of the drug, if recommended by the iSRC. The maximum oral dose in Part A will not exceed 480 mg C106.

Subjects will come for 3 visits to the Clinical Research Unit (CRU). Screening (Visit 1) will take place within 4 weeks of the planned dose (Day -28 to Day -1) and will include the subject's signing of the informed consent and an eligibility check. At Visit 2, subjects will reside at the CRU from Day -1 (the day before investigational medicinal product [IMP] administration) until Day 3 for single dose IMP administration, safety, tolerability, and PK assessments. The subjects must fast for at least 10 hours before until 4 hours after the anticipated dosing time on Day 1. During fasting, water, but no other drinks, is allowed as desired. No drinks are allowed for 1 hour before and 1 hour after dosing. The first 2 subjects in each cohort will be dosed in a sentinel fashion, 1 subject will receive C106 and the other will receive placebo as randomised. The subjects will be carefully monitored by clinical staff during and after dosing. Vital signs and ECG will be checked at regular intervals. Ambulatory ECG telemetry will be used for cardiac surveillance up to 24 hours after IMP administration. There is immediate access to equipment, qualified staff and an intensive care unit (ICU) in case of an acute emergency. To give sufficient time for observation of any reactions there will be at least 24 hours before dosing of the remaining 6 subjects, who will be dosed in groups of 3 subjects at least 24 hours apart. A final end-of-trial visit (Visit 3) will take place on Day 7 ( $\pm 2$  days) or after early withdrawal.

Cardiodynamic ECG assessments (collect and store) will be performed in all cohorts (except the first cohort A1) where C106 is given in the fasted state (*i.e.*, not in the fed period of the fasted/fed cohort) and will include serial ECG extractions at baseline (prior to dosing) and at the same time points as PK sampling during the first 24 hours post-dose.

The doses given after the starting dose and time points for safety and PK sampling may be adjusted as recommended by the iSRC following evaluation of emerging safety, tolerability, and PK data. If needed, one visit for additional safety and PK assessments may be added based on recommendations from the iSRC.

Before initiating a new dose cohort, all subjects in the previous cohort must have been treated and all available safety, tolerability, and plasma concentration data up until and including 48 hours post dose must have been evaluated by the iSRC. After collection of the last available 48-hour data, there will be at least one week between dose escalations. In case of dosed dropouts, available data for the dropouts will be included in the iSRC evaluation. Based on emerging safety and PK data, the amount of required safety and PK data to be reviewed after a completed cohort might be adjusted.

### Part A: food interaction

One dose cohort (planned to be cohort A4) will be selected to investigate any potential food interaction. The predicted maximum exposure in the food interaction cohort (taking into account a possible food interaction effect on the exposure) of the chosen dose level will not exceed the exposure tolerated in previously evaluated cohorts.

Subjects exposed to C106 during fasting conditions in the selected cohort will return to the clinic after a wash-out period of at least 5 half-lives (as determined by evaluation of PK data) to receive a second dose of C106 under fed conditions. In case of dropouts at the selected dose level, subjects may be replaced to guarantee a full cohort size for the food-interaction part of the trial (if considered necessary). Any replacers will receive active treatment. The assessments during fed conditions will be the same as during fasting conditions except that the subjects will consume a U.S. Food and Drug Administration (FDA) recommended high-fat, high calorie breakfast 30 minutes prior to IMP administration and no screening visit will be conducted. Potential replacement subjects will come for a screening visit and perform one fasting period and one fed period.

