# 8.1.1.1 Food interaction

One dose cohort (planned to be cohort A4) will be selected to investigate any potential food interaction. The predicted maximum exposure (taking into account a possible food interaction effect on the exposure) of the chosen dose level will not exceed the exposure tolerated in previously evaluated cohorts.

Subjects in the selected cohort will return to the clinic after a wash-out period of at least 5 half-lives (as determined by evaluation of PK data) to receive a second dose of C106 or placebo under fed conditions. In case of dropouts at the selected dose level, subjects may be replaced to guarantee a full cohort size for the food-interaction part of the trial (if considered necessary). Any replacers will receive active treatment. The assessments during fed conditions will be the same as during fasting conditions except that the subjects will consume an FDA recommended high-fat, high calorie breakfast 30 minutes prior to IMP administration as detailed in Section 10.5.1 and no screening visit will be conducted. Potential replacement subjects will come for a screening visit and perform one fasting cohort and one fed cohort.

The schedule of events for Part A is shown in Table 8.1-1 and detailed for Visit 2 in Table 8.1-2.

Trial assessments are described in Section 11.

Table 8.1-1 Schedule Visit Assessment	Refer to CTP section:	Screening		nterven rvation		d	Follow-up/End-of-trial		
		Visit 1 Day -28 to Day -1	Visit 2 			Visit 3			
			Admission Day -1	Day 1	Day 2	Day 3	Day 7 (±2) 		
Informed Consent	14.3	Х							
Inclusion/exclusion criteria	9.4, 9.5	Х		Х					
Demographics	11.2	Х							
Medical/surgical history	11.2.5	Х							
HIV, hepatitis B and C	11.2.7	Х							
Alcohol test	11.2.9	Х	Х						
Weight/height (BMI)	11.2.4	Х							
Serum FSH 	11.3.5	Х							
Urine Drug Screen 	11.2.8	Х	Х						
Physical Examination	11.3.2	Х		X 			Х		
Clinical Laboratory Profile 	11.3.5	Х	Х		X	X	Х		
Safety urine sampling	11.3.5	Х	Х		Х	X	Х		
Urinalysis (dipstick)	11.3.5	Х	Х				Х		
Vital Signs 	11.3.4	Х	Х	Х	X	X	Х		
12-lead safety ECG	11.3.2	Х		Х	X	X	Х		
Telemetry	11.3.3			X9					
Randomisation				Х					
IMP administration	10.5			X 					
Cardiodynamic ECG 	11.5.3			Х	X				
PK blood sampling	11.4.1			Х	Х	Х			
PK urine sampling	11.4.2			Х	X	X			
Breakfast					X	Х			
High-fat breakfast 	10.5.1			X 					

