# 9.10 Blinding

This is a double-blind trial, and the allocation of treatments will not be disclosed until clean file has been declared and the database has been locked.

The IMP, *i.e.*, the C106 and the placebo oral solutions, are identical in appearance. Both solutions are colourless to yellow. Hence, it is expected that the subjects, Investigator and other site personnel will remain unaware of treatment allocation.

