# **10.5** Treatment administration

## 10.5.1 Treatment administration Part A

Subjects in Part A (SAD) will be administered a single oral dose of either C106 or placebo as randomised. The proposed doses are 5, 30, 60, 180, 240 and 300 mg C106.

Subjects who participate in the food interaction part will be administered a second single dose of either C106 or placebo. Any replacers in the food interaction part will receive C106 and will participate in both a fasting and a fed period.

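### The synopsis and the body of the protocol disagree on who returns for the fed period; carrying out the synopsis version would disclose C106 allocation in that cohort before database lock

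*Combined protocol and SAP*

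**What the plan says.** The current text gives two accounts of the fed period.

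- **Section 1, Trial Synopsis, Part A: food interaction.** "Subjects exposed to C106 during fasting conditions in the selected cohort will return to the clinic" after the wash-out, "to receive a second dose of C106 under fed conditions". Placebo subjects are not mentioned.
- **Section 8.1.1.1, Food interaction.** "Subjects in the selected cohort will return to the clinic after a wash-out period of at least 5 half-lives", and they receive a "second dose of C106 or placebo under fed conditions".
- **Section 10.5.1, Treatment administration Part A.** "Subjects who participate in the food interaction part will be administered a second single dose of either C106 or placebo".
- **Table 8.1-1, footnote 2.** Every subject of the food-effect cohort has two intervention periods.

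On blinding, Section 9.10 says that "the allocation of treatments will not be disclosed until clean file has been declared and the database has been locked", and it expects subjects, the Investigator and other site staff to stay unaware of allocation. Section 9.11 limits code-breaking to emergencies. Section 9.11.1 lets the safety review committee break the code only for decisions on continuing dosing or stopping escalation. Section 10.4 keeps the unblinded preparation staff out of all other trial activities.

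On replacement, the synopsis and Sections 8.1.1.1, 9.8.5 and 10.5.1 agree that any replacement subject in the food-interaction part receives C106.

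**The concern.** Subjects cannot be selected for recall by C106 exposure unless someone uses the code, and no section provides for that use. Even if a person outside the site drew up the list, the invitation itself would tell the subject and the Investigator what the subject had received.

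The primary endpoint depends on investigator judgement. Causality and intensity of adverse events are graded by the Investigator, as is the clinical significance of ECG, vital-sign, laboratory and examination findings. In a fed period attended only by subjects known to be on C106, those judgements are made without the blind and with no placebo subject beside them.

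Section 17.5.1 tabulates adverse events by part, cohort, treatment and overall, and mentions no fasted/fed split. Detail is left to a separate SAP. Unless that plan separates the periods, unblinded fed-period events would share a column with blinded fasted events. In that cohort, C106 subjects would also contribute two dosing periods and placebo subjects one.

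**Working it through.** No power or sample-size formula applies. The check is a count of what each version would reveal.

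**1. Cohort structure (Sections 9.3 and 9.9).** Part A has 6 cohorts of 8: 6 × 8 = 48, the planned figure. Within a cohort, the sentinel block is 1 C106 + 1 placebo and the second block is 5 C106 + 1 placebo, giving 6 C106 + 2 placebo.

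**2. Before recall.** The placebo subject can be either of 2 in the first block and any of 6 in the second, so 2 × 6 = 12 allocations are possible. The probability of C106 is 1/2 for each sentinel subject and 5/6 for each of the other six.

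**3. After recall, no dropouts.**

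| | Synopsis | Sections 8.1.1.1 and 10.5.1, footnote 2 |
|---|---|---|
| Return for the fed period | 6 (6 C106, 0 placebo) | 8 (6 C106, 2 placebo) |
| Allocations still possible | 1 | 12 |
| Probability of C106 for a returner | 1 | unchanged (1/2 or 5/6) |
| Probability of C106 for a non-returner | 0 | not applicable |

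**4. After recall under the synopsis, with d dropouts among the C106 subjects.** There are 6 − d returners, all known to be on C106. On attendance alone, the 2 + d non-returners contain 2 placebo subjects, a share of 2/(2 + d):
- d = 0: 2/2 = 100%
- d = 1: 2/3 = 67%
- d = 2: 2/4 = 50%

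Returners are identified in every case. Attendance alone identifies all the non-returners as placebo only when d = 0.

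**5. Which judgements are exposed.** The wash-out is at least 5 half-lives. With the interim mean half-life of about 11 hours (Section 6.1.7), that is 5 × 11 = 55 hours. The last in-clinic fasted assessment is at 48 hours (Table 8.1-2). Most fasted findings would therefore be observed before a subject returns. The exposed material is the fed period, any late fasted follow-up, and any causality decision made after recall.

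**6. Share of the trial.** The cohort is 8/48 = 16.7% of Part A and 8/80 = 10% of planned subjects. It holds 2 of the 6 × 2 = 12 Part A placebo subjects.

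**7. PK comparison.** The fed/fasted contrast uses the cohort's C106 subjects, and both versions bring those subjects back.

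**The case against.** The best defence is that the operative text is consistent. Section 8.1.1.1, Section 10.5.1 and the schedule footnote all return the whole cohort, and a site working from them would recall everyone. Only the synopsis differs. This stands, and it means that a reader who infers that the plan as a whole breaks the blind goes too far: disclosure follows only if the synopsis wording is carried out. It does not remove the contradiction, because the synopsis describes a different recall rule and nothing in the protocol says which text prevails.

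Four further limits also stand.

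- A reader might infer that all 8 allocations would be known. That is the no-dropout case.
- A reader might infer that 17% of the Part A safety data would be compromised. That figure counts subjects, not judgements, and most fasted findings come before recall.
- The fed period serves a PK objective, and the safety analysis is descriptive. Losing a comparator of 2 placebo subjects costs little in formal terms.
- A reader might infer that the body text keeps the blind completely. It does not for replacement subjects, who are known to be on C106 under either version.

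The remedy may also come too late. The heading of Section 8.3.1 calls cohorts 1 to 4 completed, while Section 8.1 still describes A4 as the planned fed cohort. The documents do not show whether the fed period has been run, or under which version.

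**Conclusion.** The contradiction is real and should be corrected. It goes beyond wording, because the two texts give different fed-period samples (6 against 8 subjects with no dropouts) and only one of them can be run for the randomised subjects without disclosing allocation. Under the synopsis version every returner is unblinded before lock, with no supporting exception in Sections 9.11 or 9.11.1.

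The reach is limited to one cohort of 8, and mainly to fed-period judgements of causality, intensity and clinical significance. A reader might go on to infer that the food-effect estimate is biased by who returns. The documents do not support this, since the same C106 subjects supply it under both versions.

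The conclusion assumes 6 + 2 allocation in the chosen cohort. The claim that most fasted findings escape also assumes the interim half-life of about 11 hours and recall no earlier than the stated wash-out.

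**What to change.** 1. **Reconcile the synopsis with Section 8.1.1.1, Section 10.5.1 and footnote 2 of Table 8.1-1.** Rewording the synopsis sentence so that all subjects of the selected cohort return under their original allocation preserves the blind for the originally randomised subjects. The cost is one sentence; the two placebo subjects attend a period that the body text already describes.
2. **If the synopsis version is intended, or has already been carried out,** state in the protocol and the report that the fed period is open-label, who returned and who knew the allocation. Present fed-period safety data separately from the blinded fasted data. This costs edits to Sections 8.1.1.1, 9.10 and 10.5.1 and the footnote, plus one further set of descriptive tables.
3. **Under either version, flag replacement subjects as open-label** in the safety listings and note the exception in Section 9.10. This costs one flag and one sentence.

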# Part B (MAD):

In Part B, repeated, oral doses of C106 will be administered in 4 sequential dose cohorts. Within each cohort, subjects will be randomised to receive C106 (n=6) or placebo (n=2) in a blinded fashion. One additional dose cohort can be explored based on emerging safety, tolerability and PK of the drug if recommended by the iSRC. The initial dose, dose escalations and dosing schedule will be based on emerging safety, tolerability, and PK data observed in the SAD part of the trial (Part A) and on emerging data from the MAD part. Each dose level during Part B will be selected such that the predicted maximum exposure will not exceed the maximum exposure (based on AUC and  $C_{max}$ ) in previously evaluated SAD cohorts. The proposed doses are 40, 100, 180 and 240 mg BID. One (1) additional dose cohort can be explored based on emerging safety, tolerability and PK of the drug if recommended by the iSRC. The maximum daily oral dose in Part B will not exceed 480 mg C106 (240 mg BID). Twice daily dosing for 8 days is planned. Based on emerging PK data once daily dosing may be applied if recommended by the iSRC. The number of dosing days may be changed based on PK data from Part A (SAD), with the aim to reach steady state during the dosing period. The treatment duration will, however, not exceed the treatment duration in pre-clinical toxicology studies.

Subjects will come for 3 visits to the CRU. Screening (Visit 1) will take place within 4 weeks of the first dose (Day -28 to Day -1) and will include the subjects signing of the informed consent and an eligibility check. At Visit 2, subjects will reside at the CRU from Day -1 (the day before IMP administration) until Day 10 for 8 days IMP administration, safety, tolerability, and PK assessments. Subjects must fast from 2 hours prior to each IMP administration until 1 hour after. During fasting, water, but no other drinks, is allowed as desired. No drinks are allowed for 1 hour before and 1 hour after dosing. On Day 8, only the morning dose will be administered.

The first 2 subjects in each cohort will be dosed in a sentinel fashion, 1 subject will receive C106 and the other will receive placebo as randomised. The subjects will be carefully monitored by clinical staff during and after dosing. Vital signs and ECG will be checked at regular intervals. There is immediate access to equipment, qualified staff and an ICU in case of an acute emergency. To give

sufficient time for observation of any reactions there will be at least 24 hours before dosing of the remaining 6 subjects, who will be dosed in groups of 3 subjects at least 24 hours apart. A final end-of-trial visit (Visit 3) will take place on Day 22 ( $\pm 2$  days) or after early withdrawal.

For subjects participating in cohort B4, an assessment of endothelial function using EndoPAT will be performed before the first IMP administration (on Day -1 or 1), and  $30\pm10$  minutes after IMP administration on Day 7 (morning or evening). The EndoPAT assessments should be done at approximately the same time of the day on both occasions. Subjects must fast for at least 4 hours prior to the EndoPAT assessment until end of assessment. During fasting, water, but no other drinks, is allowed as desired. No drinks are allowed for 1 hour before and 1 hour after dosing.

Besides the starting dose and subsequent doses, also time points for safety and PK sampling may be adjusted as recommended by the iSRC following evaluation of emerging safety, tolerability, and PK data. If needed, one visit for additional safety and PK assessments may be added based on recommendations from the iSRC.

After collection of the last available 10 days data (48 hours after the last dose), there will be at least 2 weeks between dose escalations. Before initiating a new dose cohort, all subjects in the previous cohort must have been treated and all available safety, tolerability, and plasma concentration data up until and including 48 hours post dose must have been evaluated by the iSRC. In case of non-replaced dropouts, available data for the dropouts will be included in the iSRC evaluation. The iSRC may recommend including replacers to be able to make an informed recommendation on the next dose level. Based on emerging safety and PK data, the amount of required safety and PK data to be reviewed after a completed cohort might be adjusted.

